1.0 Objectives

1.1 Purpose:

We propose to develop an informatics system to assist people with memory impairment. Early stages of Alzheimer's and Alzheimer's related dementia often causes memory concerns. Persons with Memory Concern often cannot match names with faces or cannot recognize faces with a sure feeling of familiarity. Persons with Memory Concern (PWMC) may have difficulty remembering the names of family members and friends or may address them with a wrong name. They recognize the faces they see daily, such as a spouse or caregiver, but they may confuse visiting friends and grandchildren. The inability to remember names or relationships contributes to isolation and deeply affects their social lives. The proposed solution is a Smartwatch Reminder (SR) system to conspicuously provide this information to the PWMC when needed. This system will automatically transmit pictures and relevant information to a smartwatch worn by the PWMC when family or friends visit. The system will be evaluated on the target persons with memory concern population to measure engagement and improvements in social interactions and well-being.

Phase I Aims:

Aim 1: The phase I will develop a prototype SR system with limited features. It will work on one model of smartphone and smartwatch. The prototype system can be used to get feedback from potential users.

Aim 2: Examine the feasibility of the SR system for PWMC.

The result of Phase I will include user feedback that demonstrates the acceptability and perceived utility of the system.

Phase II Aims:

Aim 3: Phase II will develop smartphone and smartwatch apps designed to work with the popular products of 2022. The project will provide a smartwatch and tablet for dyads in the treatment group. Family, friends, etc. of the treatment group participants will be able to download a smartphone app from an online store. Instructional material will be created to show the suggested information that can be entered into the app.

Aim 4: Evaluate whether the Smartwatch Reminders exerts positive benefits for PWMCs' social engagement and well-being via an embedded experimental mixed methods design that combines the collection and analysis of qualitative data within a traditional randomized controlled trial (RCT) design.

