3.0 Study Endpoints/Events/Outcomes

3.1 Primary Endpoint/Event/Outcome:

Phase I: Twenty care partners will complete a system review checklist and context of care items in a dyadic interview setting. The intervention will be considered successful if at

SOCIAL PROTOCOL (HRP-580)

PROTOCOL TITLE: A Mobile Informatics Solution to Aid in Memory

VERSION DATE: 7/1/2022

least 75% of participants score an average of 4 (out of 5) points or higher on the checklist, indicating that SR met their needs (i.e., indicated agree or strongly agree that the SR was useful, acceptable, and feasible overall). This threshold has been used as a benchmark for success in prior research evaluating technological interventions for PWMC and their care partners(6-8). If the criteria for success are not met, the technology will be refined based on feedback and suggestions from PWMC and care partners, before conducting additional testing with the improved prototypes. Ample qualitative feedback will be available via the dyadic interviews to guide such refinement.

Phase II: Baseline and 6 month data will be used in a 2x2 repeated measures analysis of covariance to examine whether use of the SR results in statistically significant changes in PWMC negative health transitions and , social interaction, pleasant events, social stress, loneliness, relationship closeness, and community engagement and care partner well-being, such as social support, depression and burden (9). The primary independent variable in the proposed investigation consists of an indicator variable for random assignment into the SR treatment condition or the attention control group. Additional analyses will determine if covariates (context of care, mobile device proficiency, and dementia severity indicators) significantly vary across the SR treatment and attention control groups at baseline and over 6-months. If statistically significant variations between the SR treatment and control groups are found, baseline and/or change scores for these covariates will be included in all repeated measures analyses of covariance tests to provide additional statistical control.

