The RA will then ask the participants semi-structured questions to elicit open-ended data on the feasibility and utility of SR (see Appendix). The interview questions include prompts about technology more generally to elicit feedback about opportunities and barriers for technology to assist care partners and PWMC in navigating everyday life. This will provide a more comprehensive perspective regarding the feasibility and use of the SR system. Participants will provide in-depth information on the reasons why PWMC and care partners felt the SR will or will not be easy to use, and will point out barriers or facilitators to use that will be critical to address when refining SR prior to Phase II.

Phase I Data Collection.

18-item system review checklist. This will be completed verbally by care partners and PWMCs during the dyadic interviews. The checklist includes Likert items designed to measure both the PWMC and care partners' perceptions of the performance of SR in terms of ease of use, clarity, and quality of information provided.

Context of care. Questions will be completed verbally during the dyadic interviews. Care partners and PWMCs can complete the context of care variables. It includes items on geographic location, time since diagnosis, type of dementia diagnosis, Medicaid status, living arrangement of the PWMC, and demographics of the PWMC and the care partner.

Semi-structured questions. The RA will conduct dyadic interviews with Phase I participants to elicit open-ended data on the feasibility and utility of SR. Questions will also elicit feedback on how participants' technology use has changed due to the COVID-19

pandemic. The semi-structured questions will provide in-depth information on the reasons why PWMC and care partners felt the SR was or was not easy to use, and will point out barriers or facilitators to use that will be critical to address when refining SR prior to Phase II (33).

Phase II. Evaluate the Smartwatch Reminder Efficacy

Overview of Phase II. The primary goal of the SR is to facilitate social interaction for PWMC by providing facial recognition of family, friends, and other key people. In this Phase II study, the SR will be evaluated to determine whether it provides positive benefits for PWMC's social interactions and well-being.

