- Dementia severity. Care partners will complete validated measures of dementia severity including the PWMC's dependence on assistance with 6 activity of daily living tasks and dependence on assistance with 6 instrumental activity of daily living tasks(16-18, 50-52). An 8-item scale will assess the intensity of PWMCs' memory losses, communication deficits, and recognition failures at each time point (memory impairment)(19, 20). From the Dementia Severity Rating Scale, we are using one item about the PWMC's recognition of others (53). Additionally, during screening, the PWMC will complete the Telephone Interview for Cognitive Status (TICS-40) developed from the Aging, Demographics, and Memory Study), which will assess their level of dementia severity at the beginning of the study (50).
- Social interaction. Questionnaires will be administered to care partners to determine the frequency and quality of PWMCs' interaction in six different areas: in-person visits; telephone/video calls; traditional mail correspondence, text messaging, or email; and social media. Per the recommendations of prior research on informal long-term care, a prior week estimate will be completed that includes frequency and duration of each activity(22). A 7-day time-window was chosen as it is less prone to recall error. In addition to frequency data, satisfaction with the quality of interaction will be assessed on a simple 5-point scale, similar to prior reliable measures utilized in Alzheimer's disease and related dementias care partner intervention studies(23).
- Pleasant Events/Social Engagement. Care partners will complete the Pleasant Events Schedule-AD (PES-AD) Short Version (24, 25) for PWMCs. The PES-AD Short Version includes 20 items of events and activities for PWMCs. As originally constructed, the items of the PES-AD were within the capacity of individuals suffering from the earlier/milder stages of dementia, and thus were appropriate for inclusion in this Phase II project(24, 25). Items are rated according to their frequency during the past month and how much the PWMC enjoys the activity. An overall summary score assessing frequency of engagement in enjoyable activities is generated by multiplying each frequency and enjoyment item with each other and summing the resulting responses. The PES-AD has demonstrated excellent reliability and validity(24, 25).

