audit trail). In addition, patterns that link particular themes will be identified and discussed in successive meetings between [name] and [name] to identify more complex processes of Smartwatch use or this technology's pathways to benefit PWMC and their care partners. During monthly team meetings, the development of codes, categories, and themes will be reviewed with the other academic investigators (Drs. [name] and [name]) and the AME team to yield any additional input into these project components. The multiple team meetings and discussions will allow for an exploration of alternative interpretations of the qualitative data and will also provide a check regarding the quality and richness of the data collected during the embedded mixed methods components.

Phase II Quantitative Analysis: Data available at baseline and 6 months will allow for a 2x2 repeated measures analysis of covariance to examine whether use of the SR results in statistically significant changes in PWMC negative health transitions and , social interaction, pleasant events, social stress, loneliness, , relationship closeness, and community engagement and care partner well-being, such as social support, depression and burden (9). The primary independent variable in the proposed investigation consists of an indicator variable for random assignment into the SR treatment condition or the attention control group. IBM SPSS Statistics 21(41) will be used to conduct these analyses, as it supports a range of univariate, bivariate, and multivariate statistical analysis procedures. The team has extensive experience conducting longitudinal analyses on their prior research on dementia(5, 6, 42-44). Our proposed analyses will provide in-depth tests of the study hypotheses. Outcomes will include statistical significance of within-subjects, or 6-month change, in those in the Smartwatch Reminder treatment or control groups on key outcome variables (see above). Additional analyses will determine if covariates (context of care, mobile device proficiency, and dementia severity indicators) significantly vary across the SR treatment and attention control groups at baseline and over 6-months. If statistically significant variations between the SR treatment and control groups are found, baseline and/or change scores for these covariates will be included in all repeated measures analyses of covariance tests to provide additional statistical control.

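### Recognising people is the SR's stated mechanism, yet it is not a prespecified outcome; its measures are severity covariates, so a recognition benefit would be read as imbalance

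*Combined protocol and SAP*

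**What the plan says.** Section 1.1 states the problem: "Persons with Memory Concern often cannot match names with faces or cannot recognize faces with a sure feeling of familiarity". It adds the consequence: "The inability to remember names or relationships contributes to isolation and deeply affects their social lives". The Phase II overview in section 5.2 gives the remedy: "The primary goal of the SR is to facilitate social interaction for PWMC by providing facial recognition of family, friends, and other key people". Social interaction is therefore the goal, and help with recognising people is the means.

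The Phase II outcome list in section 3.1, repeated in substance in 17.1, opens with negative health transitions and continues with "social interaction, pleasant events, social stress, loneliness, relationship closeness, and community engagement and care partner well-being, such as social support, depression and burden". Recognition is not in it.

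Recognition is measured all the same, in the Dementia severity bullet of section 5.2. One measure is a single borrowed item: "From the Dementia Severity Rating Scale, we are using one item about the PWMC's recognition of others". The other is part of a memory-impairment scale: "An 8-item scale will assess the intensity of PWMCs' memory losses, communication deficits, and recognition failures at each time point".

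Sections 3.1 and 17.1 give severity indicators one role. The plan tests whether "covariates (context of care, mobile device proficiency, and dementia severity indicators) significantly vary across the SR treatment and attention control groups at baseline", and again over the 6 months. If a significant difference appears, baseline scores, change scores or both go into every outcome model.

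**The concern.** The plan tests the far end of a causal chain and names no outcome for its first link. If the social outcomes show no difference, two explanations need separating: the reminders did not help people know who was with them, or they helped and contact did not change. The first calls for a better device, the second for a different idea of what drives isolation. If the social outcomes do improve, nothing prespecified ties the gain to recognition.

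Section 3.2 hopes to suggest how and why benefit arises. The other sources for that are use logs, the system review with its open-ended answers, and 20 interviews. All come from dyads given the SR, so none gives a randomised comparison.

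The classification has a second effect. An arm difference in recognition is what a working device should produce, yet the plan would handle it as a nuisance.

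**Working it through.** **1. The plan's own figure.** Section 17.2 gives 97 dyads for f² = 0.15, alpha 0.05, power 0.80 and 6 predictors. With a noncentral F test (u = 6, v = N − 7, λ = 0.15N), power is 0.798 at N = 97 and 0.813 at N = 100, and it first reaches 0.80 at N = 98. The figure reproduces to within one dyad. It does not concern recognition; it serves here only to fix the sample size at 100, or 50 per arm.

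**2. Outcomes against measures.** Section 3.1 names ten domains: health transitions, social interaction, pleasant events, social stress, loneliness, closeness, community engagement, and care partner support, depression and burden. As section 5.2 describes the instruments, none rates recognition. The two measures that do are both under Dementia severity.

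**3. What the covariate role can do.** Let *a* be the SR's effect on recognition change (in SD), *b* the slope of a social outcome on recognition, and *c* any effect by another route. The randomised effect is c + ab. After adjustment for recognition change it is c. The documents give none of these values, so the range below is assumed. The last three columns come from 2,000 simulated trials per row with 50 dyads per arm.

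| a | b | c | c + ab | Mean unadjusted | Mean adjusted | Trials with p < 0.05 on recognition |
|---|---|---|---|---|---|---|
| 0.3 | 0.3 | 0 | 0.09 | 0.088 | −0.002 | 0.315 |
| 0.5 | 0.5 | 0 | 0.25 | 0.255 | 0.002 | 0.703 |
| 0.8 | 0.5 | 0 | 0.40 | 0.397 | 0.001 | 0.975 |
| 0.3 | 0.3 | 0.2 | 0.29 | 0.284 | 0.191 | 0.3325 |
| 0.8 | 0.5 | 0.2 | 0.60 | 0.596 | 0.201 | 0.9755 |

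The adjusted column applies the adjustment in every simulated trial. The last column is how often the plan's significance check would call for it. A normal approximation agrees: the noncentrality is a√(50/2) = 5a, so for a = 0.3, 0.5 and 0.8 the power is Φ(1.5 − 1.96) = 0.32, Φ(2.5 − 1.96) = 0.71 and Φ(4.0 − 1.96) = 0.98.

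The better the device works on recognition, the more likely the adjustment. An effect that runs wholly through recognition then falls to about zero. This assumes that recognition is scored on its own and that the change score is the one entered. If recognition enters only within the 8-item total, both the trigger and the loss would be diluted.

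**4. Precision if recognition were an outcome.** The detectable standardised difference at two-sided 0.05 and 80% power is (1.96 + 0.84) × √(4/N) × √(1 − ρ²), where ρ is the assumed correlation with baseline.

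- N = 100: 0.56 (ρ = 0), 0.49 (ρ = 0.5), 0.40 (ρ = 0.7).
- N = 97: 0.57, 0.49, 0.41.

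With no gain from baseline, power for a 0.5 SD difference at 50 per arm is 0.71.

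**The case against.** The strongest reply is that an arm comparison already exists. Sections 3.1 and 17.1 test severity indicators between arms over follow-up, and on the plan's own filing the recognition measures are among them. A reader might infer that the trial cannot tell a device that fails from one that works without changing social life. The documents do not support that: the 8-item scale is collected at each time point in the survey given to both arms, so the data would exist. What stands is narrower. The comparison is a covariate check, and its stated consequence is adjustment, not a reported result.

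A reader might also infer that the device is meant to restore recognition. The documents describe an external aid that supplies pictures and information, with social interaction as the goal. Leaving a mechanism out of the outcomes is a permissible choice. It is a weak one here because the means is stated so plainly, and because the measures are placed where they can act against the outcomes.

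Three limits on any repair also stand:

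- The survey wording is not available, so it is unknown whether a person who reads a name from the watch is rated as recognising the visitor. If ratings are of unaided recognition, a null on them would not show that the device failed.
- Care partners know their arm, so a difference could partly reflect expectation.
- Follow-up timing of the borrowed item is not stated separately, and shortened surveys after a death or a move to long-term care may lose some ratings.

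Finally, the mechanism evidence is more than 20 interviews. It also includes use logs, open-ended review answers and the planned analyses of use against outcomes, but none of these is randomised.

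**Conclusion.** The point holds as a gap in prespecification that should be closed. Recognition is the SR's stated means, it is in none of the ten named outcome domains, and both of its measures are used only as covariates. A null or positive social result would therefore have no prespecified randomised efficacy comparison on the first link. A real recognition benefit could be treated as imbalance and adjusted out of every outcome model. Under the assumed effects above, that takes a wholly mediated benefit of 0.09 to 0.40 SD to about zero.

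The size of that loss rests on assumed effects and on the plan's open choice between baseline and change scores. The absence of recognition from the outcome lists rests on the text alone. It does not follow that the data could not answer the question, or that a recognition outcome would settle the mechanism.

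**What to change.** In sections 3.1 and 17.1:

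- Take the recognition items out of the severity covariates. At minimum, bar their post-baseline and change scores from any outcome model, including where they sit inside the 8-item total.
- Name the between-arm difference in care-partner-rated recognition at 6 months (and at 3 months), adjusted for its baseline, as a supportive proximal secondary outcome. Use the recognition items of the 8-item scale, plus the Dementia Severity Rating Scale item if it is collected at follow-up.
- Keep the TICS-40 and the activity and instrumental activity of daily living measures as the severity indicators.
- State whether the existing wording captures recognition with the watch or without it, and interpret the result accordingly. Do not change item instructions now: version 19 and its timeline changes suggest that enrolment is under way, and baselines may already be rated under the current wording.

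The cost is a text amendment, with no new instrument or visit. The downside is one more secondary test on a coarse rating from an unblinded rater, with the modest precision shown in step 4 of the working. It should be reported as supporting evidence of mechanism only.
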